#### 5.7.2. TREATMENT OF BREAKTHROUGH ANGIOEDEMA ATTACKS

A breakthrough attack is defined as an angioedema attack that occurs during long-term prevention therapy with CINRYZE® (i.e, between first study drug and last study drug dose).

The following efficacy endpoints for treatment of breakthrough angioedema attacks will be assessed by CINRYZE® treated attacks, non-CINRYZE® C1-INH treated attacks and all other attacks (including any medications other than C1-INH and untreated attacks):

- The number of subjects with breakthrough angioedema attacks.
- The number of subjects with 1, 2, 3 or more angioedema attacks.
- The number of subjects who achieve initial improvement and Complete Resolution.
- Time to initial improvement and time to Complete Resolution.

Additional analysis for breakthrough angioedema attacks treated with CINRYZE® will also be presented for:

- The number of subjects with breakthrough angioedema attacks.
- The number of subjects with 1, 2, 3 or more angioedema attacks.
- Time from onset of attack to time treated by CINRYZE.
- The number of subjects who achieve initial improvement and Complete Resolution. Complete Resolution is defined as the cessation of all symptoms of the breakthrough angioedema attack since onset of attack.
- Time from the start of study drug administration, CINRYZE°, for the particular attack to the time of initial improvement and time to Complete Resolution.

\\SW20RND01\\VistaTempDir\Temp28232\Shire\_0624\_209\_SAP\_v1 0.docx Document: Version Number:

Version Date: 21Jul2017

Template No: CS\_TP\_BS016 Revision 4

Effective Date: 01Apr2016

Author:

Copyright © 2009, 2010, 2012, 2016 Quintiles Transnational Corp. All rights reserved.

The contents of this document are confidential and proprietary to Quintiles Transnational Corp. Unauthorized use, disclosure or reproduction is strictly prohibited.

Shire
PROTOCOL: 0624-209
Page 18 of 35

Derivations will be constructed as follow:

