- c: Subjects may initiate the practice of self-administration with direct supervision by the Investigator or qualified delegate.
- d: Self-administration supervised by the Investigator or qualified delegate at the study site may continue after Dosing Visit 8 until the subject (or caregiver) feels confident with the technical and medical aspects and is deemed independent for self-administration. Details regarding self-administration will be documented and entered in CRF.
- e: When deemed independent (ie, subjects [or caregivers] are able to correctly reconstitute study drug, access a vein for infusion, and successfully administer the drug on at least 2 consecutive training visits), a subject may elect to self-administer doses of investigational product at home or at the study site. The Investigator's acknowledgement that a subject is certified for independent self-administration will be entered in the CRF.
- f: Subjects (or caregivers) will be allowed to self-administer at the study site. The Investigator or qualified delegate will be available for follow-up training if any of the necessary skills on self-administration have not been retained and to address any issues from the subject's perspective.
- g: Study personnel will contact the subject (or caregivers) by telephone to check on study compliance/competency with self-administration, document any AEs, and update any concomitant medications. Telephone contact will be documented in the source notes at the study site.

See Schedule 3 for clinical study assessments at the Early Discontinuation Visit (if applicable) and the 1-Week and 1-Month Post-treatment Follow-up Visits.

Page 26 30 Aug 2016

Protocol 0624-209 with Amendments 1, 2, 3, 4, and 5 CINRYZE (C1 inhibitor [human])

Schedule 3: Clinical Study Assessments – Early Discontinuation Visit and 1-week and 1-month Post-treatment Follow-up Visits

| Procedure | Early Discontinuation Visit ^a [If Applicable] | 1-Week (±1 day) Post-treatment Visit [All Subjects] | 1-Month (30 ±2 days) Post-treatment Visit [All Subjects] |
|--|---|---|--|
| Physical exam update | X | | |
| Concomitant/post-treatment medications | X | X | X |
| Body weight | X | | |
| Vital signs (BP, pulse) b | X | | |
| Hematology and clinical chemistry | X | | |
| Urinalysis with microscopy | X | | |
| Coagulation (PT, aPTT, INR) | X | | |
| Pregnancy testing ^c | X | | |
| Daily angioedema attack monitoring and study diary | X ^d | X | |
| Adverse events/SAEs ^e | X | X | X |

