Throughout the trial, a study diary will be used by subjects (or caregivers) to record specific information about any angioedema attack symptoms and details on the self-administration of investigational product (see Section 6.11). Because of the potential to precipitate an angioedema attack, subjects will be requested to postpone elective medical procedures (eg, dental work) and avoid other known attack triggers while participating in the study (see Section 6.10).

Safety will be assessed by monitoring adverse events and changes in physical examinations, vital signs, and clinical safety laboratory testing. In addition, subjects will be monitored for the development of antibodies to C1 INH. If clinically indicated, study personnel may perform examinations to actively monitor subjects for possible venous thromboembolism or other thrombotic or thromboembolic (T/TE) events. Stopping rules are provided in Section 5.5.

Protocol 0624-209 with Amendments 1, 2, 3, 4, and CINRYZE (C1 inhibitor [human])

In this study, angioedema attacks will not be reported as adverse events unless the attack meets the definition of a serious adverse event (see Section 9.1.4).

Adverse events will be recorded from the time the informed consent is signed through 7 days after the last dose of investigational product. This includes events occurring during the screening phase of the study, regardless of whether or not the investigational product is administered. In addition, the investigator will report all SAEs that occur through 30 days after the last dose of investigational product to PAREXEL International Pharmacovigilance and the respective Independent Reviewing Authority according to local reporting requirements.

Post-treatment follow-up visits will be performed 1 week (± 1 day) and 1 month (30 ± 2 days) after the last dose of study drug. If a subject prematurely discontinues investigational product, regardless of the reason, the Early Discontinuation Visit procedures listed in Schedule 3 are to be performed as completely as possible. Whenever possible, all discontinued subjects should also complete the 1-Week and 1-Month Post-treatment Follow-up visits.

The schedules of study procedures are provided as follows:

- Schedule 1: Clinical Study Assessments Screening and Treatment Period;
- Schedule 2: Investigational Product and Self-administration Training;

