6.12.1 Treatment of Breakthrough Angioedema Attacks

A breakthrough attack is defined as an angioedema attack that occurs during long-term prevention therapy with CINRYZE. If a subject receives CINRYZE for treatment of a breakthrough angioedema attack, they should continue their protocol-defined treatment schedule without alteration regardless of when the supplemental dose is administered.

If a breakthrough angioedema attack occurs during the 12-week treatment period through 1-week post-treatment, a supplemental dose of CINRYZE may be administered by IV infusion for treatment of the attack either by the Investigator (or qualified delegate) or subject (or caregiver) if trained and deemed independent to self-administer (1000 U for subjects ≥6 years of age or 500 U for subjects 2-5 years of age). If the subject does not adequately respond to the initial dose within 1 hour, a second dose of CINRYZE may be administered (1000 U for subjects ≥6 years of age or 500 U for subjects 2-5 years of age).

It is recommended that treatment of breakthrough attacks occurs at the investigational site whenever possible so that clinical assessments can be completed as specified. It is preferred that subjects receive CINRYZE within 4 hours but not more than 8 hours after the onset of breakthrough attack symptoms if treatment can occur at the investigational site.

Subjects (at least 12 years of age or their caregivers) who have completed the required self-administration training and deemed independent (per criteria specified in Section 5.3.1) may elect to self-administer CINRYZE for a breakthrough attack. Note: Subjects (or caregivers) who are participating in self-administration training and not yet qualified as independent cannot self-administer CINRYZE for a breakthrough attack; rather they must seek treatment at the investigational site. If a subject (or caregiver) who self-administers CINRYZE for treatment of a breakthrough attack does not respond adequately after instructed treatment (ie, 2 doses separated by 1 hour), they should notify the Investigator and seek medical attention or report to study site to seek further treatment and relief of symptoms.

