7.6.2 Treatment of Breakthrough Angioedema Attacks

The following efficacy endpoints for treatment of breakthrough angioedema attacks will be assessed by CINRYZE-treated attack number:

- The number of subjects who achieve Clinical Relief. Clinical Relief is defined as a sustained reduction from pre-infusion in the attack severity within 4 hours after initiation of treatment with CINRYZE.
- Time to onset of Clinical Relief.
- The number of subjects who achieve Complete Resolution. Complete Resolution is defined as the cessation of all symptoms of the breakthrough angioedema attack.
- Time to Complete Resolution.

Other analyses may be performed to establish context of the efficacy results from this study with previous Phase 3 CINRYZE studies.

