#### 4.2.2. TREATMENT OF BREAKTHROUGH ANGIOEDEMA ATTACKS

The following efficacy endpoints for treatment of breakthrough angioedema attacks will be assessed by; CINRYZE® treated attacks, non-CINRYZE® C1-INH treated attacks and other attacks (including any medications other than C1-INH and untreated attacks):

- The number of subjects with breakthrough angioedema attacks.
- The number of subjects with 1, 2, 3 or more angioedema attacks.
- The number of subjects who achieve initial improvement and Complete Resolution. Complete Resolution
  is defined as the cessation of all symptoms of the breakthrough angioedema attack since onset of attack.
- Time to initial improvement and time to Complete Resolution.

Document: \SW20RND01\VistaTempDir\Temp28232\Shire 0624 209 SAP v1 0.docx

Author: PPD Version Number: 1.0
Version Date: 21Jul2017

Template No: CS\_TP\_BS016 Revision 4 Reference: CS\_WI\_BS005

Effective Date: 01Apr2016

Elicolive Date: 017 przo 10

PROTOCOL: Page 11 of 35

Additional analysis for breakthrough angioedema attacks treated with CINRYZE® will also be presented for:

- The number of subjects with breakthrough angioedema attacks.
- The number of subjects with 1, 2, 3 or more angioedema attacks.
- Time from onset of attack to time treated by CINRYZE.
- The number of subjects who achieve initial improvement and Complete Resolution. Complete Resolution is defined as the cessation of all symptoms of the breakthrough angioedema attack since onset of attack.
- Time from the start of study drug administration, CINRYZE, for the particular attack to the time of initial improvement and time to Complete Resolution.

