#### 6.2. CHANGES FROM THE ANALYSES PLANNED IN THE PROTOCOL

Due to insufficient data collection, the analysis of clinical relief has not been conducted as planned.

\\SW20RND01\\VistaTempDir\Temp28232\\Shire\_0624\_209\_SAP\_v1 0.docx PPD Version Number: Document: Author:

Version Date: Reference: CS\_WI\_BS005

Template No: CS\_TP\_BS016 Revision 4

Effective Date: 01Apr2016

Copyright © 2009, 2010, 2012, 2016 Quintiles Transnational Corp. All rights reserved.

Shire
PROTOCOL: 0624-209
Page 27 of 35

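### SAP 5.7.2 closes the breakthrough-attack window at the last study drug dose, leaving out the post-treatment week in which the protocol still treats breakthrough attacks with CINRYZE

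*SAP*

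**What the plan says.** Protocol 6.12.1 opens with a definition: "A breakthrough attack is defined as an angioedema attack that occurs during long-term prevention therapy with CINRYZE". It gives no end day. The next paragraph of the same section then uses the term for a longer period: "If a breakthrough angioedema attack occurs during the 12-week treatment period through 1-week post-treatment, a supplemental dose of CINRYZE may be administered".

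Data collection matches the longer period. Schedule 3 marks "Daily angioedema attack monitoring and study diary" at the 1-Week Post-treatment Visit, which protocol Section 3 times at 1 week ± 1 day after the last dose. Protocol 7.6.2 says that the treatment endpoints "will be assessed by CINRYZE-treated attack number" and names no cut-off at the last dose.

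SAP 5.7.2 repeats the protocol's definition and adds a gloss that limits breakthrough attacks to those "between first study drug and last study drug dose". It does not say which kind of dose is meant. SAP 6.2, which lists departures from the protocol's analyses, contains one entry: "Due to insufficient data collection, the analysis of clinical relief has not been conducted as planned". The window is not mentioned there.

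**The concern.** The protocol lets a subject who has an attack in the week after the last prevention dose receive CINRYZE for it, asks for the same post-infusion assessments, and calls it a breakthrough attack. Under SAP 5.7.2 that attack is not a breakthrough attack and has no place in the three treatment-of-attack summaries: CINRYZE-treated, treated with another C1-INH, and not treated with C1-INH.

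The cut is abrupt. An attack starting one day after Dose 23 counts and one starting one day after Dose 24 does not, although both subjects are within a normal 3- or 4-day dosing interval. The half-life of functional C1 INH activity in protocol 1.1.2 is about 60 h, so at 60 / 24 = 2.5 days after Dose 24 about half of the added activity would remain.

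At stake are usable treated attacks in a very small dataset, and a treatment-of-attack result that leaves out part of the period in which the protocol offers the treatment.

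**Working it through.** **1. Reproduce the schedule.** Twice weekly for 12 weeks gives 2 × 12 = 24 doses, as in protocol 5.5.2 and Schedule 2. The mean gap is 7 / 2 = 3.5 days, as in SAP 5.8.8.

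**2. Length of the SAP window** (last dose read as last prevention dose). There are 23 gaps, so 23 × 3.5 = 80.5 days from first to last dose. Alternating gaps of 3 and 4 days give 80 or 81. SAP 5.8.8 equates 12 weeks with 84 days, so the window closes 3 to 4 days short of 84.

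**3. Length of the protocol window.** This adds the post-treatment week, with the ±1 day visit allowance as a range.

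| Days after last dose | Total window (days) | Share left out by the SAP |
|---|---|---|
| 6 | 86.5 | 6 / 86.5 = 6.9% |
| 7 | 87.5 | 7 / 87.5 = 8.0% |
| 8 | 88.5 | 8 / 88.5 = 9.0% |

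**4. Number of attacks this could involve.** The documents give no attack rate for the post-treatment week and no share treated with CINRYZE, so both are assumptions for scale. The rates used are the entry minimum of 1 per month (protocol 4.1, with a 30.4-day month) and the overseas 12-week rates of 6.3 on CINRYZE and 12.8 on placebo (protocol 1.1.2). Expected attacks = daily rate × 7 days × 6 subjects. The chance of at least one is 1 − exp(−expected), assuming Poisson counts.

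| Assumed rate | Expected attacks | Chance of at least one | CINRYZE-treated, if 25% to 100% are |
|---|---|---|---|
| 1 per 30.4 days | 42 / 30.4 = 1.4 | 0.75 | 0.35 to 1.4 |
| 6.3 per 84 days | 42 × 6.3 / 84 = 3.2 | 0.96 | 0.8 to 3.2 |
| 12.8 per 84 days | 42 × 12.8 / 84 = 6.4 | 0.998 | 1.6 to 6.4 |

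On the lowest rate, anything from no lost treated attack to one or two is plausible.

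**5. Which outputs are exposed.**
- *Subject and attack counts by treatment category (SAP 5.7.2):* directly. A subject whose only CINRYZE-treated attack is late disappears from the CINRYZE table, which is one-sixth of the minimum number of completers.
- *Kaplan-Meier analyses:* the SAP's rule under Time to Complete Resolution uses only the first attack per subject that meets the treatment criterion. A late attack matters only if it is that first one.
- *Normalized number of attacks and the 50%, 70% and 90% responder counts:* SAP 5.7.1 defines these over the treatment period, not through the breakthrough definition. No effect follows from the text.

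**The case against.** The best defence is that the SAP merely makes the protocol's definition precise. The defining sentence speaks of attacks during prevention therapy, and the objectives in protocol Section 2 repeat it. The reference to the following week sits in a sentence about permission to treat, and protocol 7.6.2 states no analysis window. On this view no planned window was changed and SAP 6.2 had nothing to declare.

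Part of this stands. The looseness starts in the protocol, and restricting the analysis to attacks on prophylaxis is a legitimate choice if it is stated. It does not settle the matter. The protocol itself calls attacks in that week breakthrough attacks. The SAP's end point also tracks prevention therapy poorly: it shuts out the dosing interval after Dose 24, yet it would include attacks during an interruption of up to 30 days after a thrombotic event if dosing later resumed (protocol 5.5.2).

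A reader might infer that the window depends on whether an attack was treated. SAP 4.2.2 describes an attack infusion as study drug: "Time from the start of study drug administration, CINRYZE, for the particular attack to the time of initial improvement". A supplemental dose after Dose 24 would then become the last dose and bring its own attack inside, while an untreated attack on the same day stayed outside. The wording leaves room for this, but the reading is strained. The gloss explains prevention therapy, and the SAP separates prevention doses from breakthrough-treatment doses in 5.6 and 5.7.1.

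A reader might go further and infer that such a dose would lengthen the period for the normalized attack rate and cost a subject responder status. That needs the strained reading plus a rule that any last dose ends that period. The formula in SAP 5.7.1 is not legible in the text available, and no readable sentence gives such a rule.

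It is also fair to say that late attacks need not vanish from the report. The subject-level attack listings in SAP Appendix I are planned on all treated subjects with no stated cut-off.

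**Conclusion.** The mismatch is real and should be corrected. It is moderate in size. Read naturally, SAP 5.7.2 leaves out CINRYZE-treated attacks starting in the 7 days after the last prevention dose, about 8% of the period in which the protocol allows that treatment (6.9% to 9.0% with the visit allowance). The share is calendar time, not a shift in any result. It rests on 24 doses given on schedule and on the post-treatment week being counted from the last dose.

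The main effect is on descriptive subject and attack counts, with a possible effect on time-to-event estimates when a subject's first qualifying attack is late. The documents do not support the claim that the treatment-of-attack results as a whole miss the intended attacks: at most a final-week subset is lost. The attack numbers above rest on assumed rates, and the verdict does not depend on them.

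**What to change.** In SAP 5.7.2:
- Define the window for the treatment-of-attack analyses as onset from the first prophylactic dose through 7 days after the last scheduled prophylactic dose, whatever treatment the attack received.
- State that a supplemental dose never sets the last study drug dose.
- Flag attacks starting after the last prophylactic dose, or tabulate them separately, so that results on prophylaxis alone can still be read.

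If the sponsor prefers the narrower window, define the last dose explicitly and list the choice in SAP 6.2 with its reason. Either way, the definition and the longer period in protocol 6.12.1 must be reconciled. This concerns which attacks are analysed and takes no position on how long attack treatment should be offered.

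The cost is SAP wording and one flag, since the protocol already plans diary and infusion data for that week. There are two drawbacks. A few attacks from a period of falling drug levels enter the tables, which the flag makes visible. Diary data for that week may also be incomplete for early discontinuers: Schedule 3 asks them for a diary entry on the day of discontinuation and for the 1-Week visit only where possible.

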#### **Complete Resolution**

Complete Resolution is defined as the cessation of all symptoms of the breakthrough angioedema attack since onset of attack.

#### **Time to Complete Resolution**

Time to complete resolution is defined as the time from the onset of attack to complete resolution of symptoms.

The analysis of the time to event endpoint includes only the first attack from each subject meeting the treatment criterion since attacks experienced by the same subject are dependent. Median time to complete resolution and the corresponding 95% CI estimated using the Kaplan-Meier method will be summarized.

Kaplan Meier plots for time from CINRYZE® to initial improvement and to complete resolution will also be presented.

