1.1.2 Clinical Experience

The overseas development program for IV CINRYZE included 2 multicenter studies of CINRYZE for prevention of angioedema attacks (1 double-blind, placebo-controlled study and 1 open-label study) and 2 multicenter studies of CINRYZE for treatment of angioedema attacks (1 double-blind, placebo-controlled study and 1 open-label study). All 4 studies were conducted in the US (LEVP 2005-1/A, LEVP 2005-1/B, LEVP 2006-1, and LEVP 2006-4). In the double-blind, placebo-controlled prevention study (LEVP 2005-1/B), CINRYZE was shown to reduce the incidence of angioedema attacks in 22 subjects analyzed (mean normalized 12-week angioedema attack rate: 6.3 for CINRYZE vs. 12.8 for placebo; p<0.0001). In the double-blind, placebo-controlled treatment study (LEVP 2005-1/A), subjects receiving CINRYZE achieved beginning of unequivocal relief of the defining attack symptom at a rate 2 times greater than subjects receiving placebo (p=0.017 for the Efficacy Dataset of 68 subjects [35 CINRYZE, 33 placebo]).

Protocol 0624-209 with Amendments 1, 2, 3, 4, and CINRYZE (C1 inhibitor [human])

receiving placebo (p=0.017 for the Efficacy Dataset of 68 subjects [35 C CINRYZE INRYZE, 33 placebo]).

More than 14,500 IV infusions of CINRYZE were administered to 262 unique subjects in 8 completed clinical studies in the overseas development program for IV CINRYZE. The vast majority of infusions were doses of 1000 U. In the placebo-controlled study with the longest administration period (LEVP 2005-1/B, prevention of angioedema attacks), 1000 U of IV CINRYZE was administered every 3 or 4 days for 12 weeks. In this study, the only CINRYZE related treatment-emergent adverse events that occurred in more than 1 subject were viral upper respiratory tract infection and rash, each occurring in 3 subjects (12%). Across studies, there were only occasional reports of infusion site pain, bruising, rash, or related localized conditions. No subjects were discontinued from CINRYZE due to an adverse event in any of the studies.

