# 3.2. DETERMINATION OF SAMPLE SIZE

A sufficient number of subjects will be enrolled to ensure that a minimum of 6 subjects complete the study. When 6 subjects have completed the 12-week treatment period, no further subjects will be enrolled; however, all subjects already enrolled in the study will be followed to study completion.

Document: \\SW20RND01\VistaTempDir\Temp28232\Shire\_0624\_209\_SAP\_v1 0.docx
Author: Version Number:

Version Date: 21Jul2017

Template No: CS TP BS016 Revision 4

Effective Date: 01Apr2016

Converight @ 2000, 2010, 2012

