#### 9.1.3. LIST OF PLANNED LISTINGS

Listing 16.2.1.1 Subject Disposition (All Enrolled Subjects)

Document: \\SW20RND01\\VistaTempDir\Temp28232\\Shire\_0624\_209\_SAP\_v1 0.docx

Author: PPD Version Number: 1.0
Version Date: 21Jul2017

Template No: CS TP BS016 Revision 4 Reference: CS WI BS005

Shire
PROTOCOL: 0624-209
Page 31 of 35

Listing 16.2.1.2 Subjects Who Terminated from the Study (All Enrolled Subjects)

Listing 16.2.2.1 Deviations from Inclusion/Exclusion Criteria (All Enrolled Subjects)

Listing 16.2.2.2 Protocol Deviations (All Enrolled Subjects)

Listing 16.2.4.1 Subject Demographic and Baseline Characteristics (Intent-to-Treat Safety Analysis Set)

Listing 16.2.4.3.1 Hereditary Angioedema (HAE) History (Intent-to-Treat Safety Analysis Set)

Listing 16.2.4.3.2 Hereditary Angioedema (HAE) History Detail (Intent-to-Treat Safety Analysis Set)

Listing 16.2.4.3.3 Medical History (Intent-to-Treat Safety Analysis Set)

Listing 16.2.4.4.1 Prior and Concomitant Medications (Intent-to-Treat Safety Analysis Set)

Listing 16.2.4.4.2 Concomitant Medical/Surgical Procedures (Intent-to-Treat Safety Analysis Set)

Listing 16.2.5.2.1 Study Drug Administration (Intent-to-Treat Safety Analysis Set)

Listing 16.2.5.2.2 Study Drug Exposure (Intent-to-Treat Safety Analysis Set)

Listing 16.2.5.3 C1-INH Antigen, Functional C1-INH activity, Complement C4 and C1q (Intent-to-Treat Safety Analysis Set)

Listing 16.2.5.4 Antibody Results (Intent-to-Treat Safety Analysis Set)

Listing 16.2.6.1 Subject Data of Angioedema Attack (Intent-to-Treat Safety Analysis Set)

Listing 16.2.6.2 Subject Data of Breakthrough Attack (Intent-to-Treat Safety Analysis Set)

Listing 16.2.6.3 Investigator Assessment of Breakthrough Attack (Intent-to-Treat Safety Analysis Set)

Listing 16.2.6.4 Self-administration Survey (Intent-to-Treat Safety Analysis Set)

Listing 16.2.6.5 Treatment Compliance (Intent-to-Treat Safety Analysis Set)

Listing 16.2.7.1 Adverse Events (Intent-to-Treat Safety Analysis Set)

Listing 16.2.7.2 Serious Adverse Events (Intent-to-Treat Safety Analysis Set)

Listing 16.2.8.1.2 Clinical Laboratory Test Results (Intent-to-Treat Safety Analysis Set)

Listing 16.2.8.1.3 Subjects with Potentially Clinically Important Laboratory Test Results (Intent-to-Treat Safety Analysis Set)

Listing 16.2.8.2.1 Vital Signs (Intent-to-Treat Safety Analysis Set)

Listing 16.2.8.2.2 Subjects with Potentially Clinically Important Vital Signs (Intent-to-Treat Safety Analysis Set)

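### The SAP plans no summary of response by CINRYZE-treated attack number, although the protocol specifies one, and SAP 6.2 does not declare the change

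*SAP*

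**What the plan says.** Protocol 7.6.2 lists four endpoints for the treatment of breakthrough attacks: the number of subjects with Clinical Relief, the time to it, the number with Complete Resolution, and the time to that. All four "will be assessed by CINRYZE-treated attack number", which reads naturally as separate results for a subject's 1st, 2nd, 3rd and later treated attacks. The synopsis says the same.

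SAP 4.2.2 and 5.7.2 group the results differently: the endpoints "will be assessed by CINRYZE® treated attacks, non-CINRYZE® C1-INH treated attacks and all other attacks". They add a frequency count, "The number of subjects with 1, 2, 3 or more angioedema attacks", and a further set of CINRYZE-treated results timed from the start of the dose given for the attack. Under Time to Complete Resolution, the time-to-event analysis "includes only the first attack from each subject meeting the treatment criterion since attacks experienced by the same subject are dependent", with a Kaplan-Meier median and 95% confidence interval.

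In SAP Appendix I, the three breakthrough-attack tables (14.2.2.1.1 to 14.2.2.1.3) are split by type of treatment. The two Kaplan-Meier figures run from CINRYZE dosing to improvement and to resolution. None of these outputs is by attack number. SAP 6.2 declares one change from the protocol: "Due to insufficient data collection, the analysis of clinical relief has not been conducted as planned".

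**The concern.** The treatment effect of CINRYZE on breakthrough attacks is a stated objective in both documents. The protocol planned to show it attack by attack, so that a reader could see whether a second or third treated attack responded as the first did. The SAP removes that view and does not say so.

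The count of subjects with 1, 2, 3 or more attacks does not replace it, because it gives frequency and not outcome. The counts of subjects who improve or resolve are not limited to first attacks. However, the SAP gives no rule for a subject whose attacks end differently, so they cannot show response on repeat treatment either.

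**Working it through.** **No figure to reproduce.** The sample size is a minimum number of completers ("A sufficient number of subjects will be enrolled to ensure that a minimum of 6 subjects complete the study"), with no power or precision target, and neither document counts treated attacks. The share left out of the time-to-event analysis can only be bracketed.

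**Inputs**

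- Subjects: 6, for illustration.
- On-treatment attack rate: the only figure given is from the overseas placebo-controlled prevention study, "mean normalized 12-week angioedema attack rate: 6.3 for CINRYZE vs. 12.8 for placebo". The ratio is 6.3/12.8 = 0.49.
- Entry floor: one attack per month (Protocol 4.1). With the SAP's 30.4-day month, 84/30.4 = 2.76 attacks per 12 weeks.
- Share of attacks treated with CINRYZE: not given, and treatment is optional (Protocol 6.12.1). Assumed 100%, 50% and 25%.

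**Formula.** Let L be the mean number of CINRYZE-treated attacks per subject, with Poisson counts. Expected first attacks per subject are 1 − exp(−L), so the share left out is 1 − (1 − exp(−L))/L. For example, at L = 6.3 this is 1 − 0.998/6.3 = 84%. At L = 0.34 it is 1 − 0.288/0.34 = 15%.

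| Assumed attacks per 12 weeks | All treated | Half treated | Quarter treated |
|---|---|---|---|
| 6.3 (overseas CINRYZE arm) | 84% | 70% | 50% |
| 2.76 (entry floor, no prophylactic effect) | 66% | 46% | 28% |
| 2.76 × 0.49 = 1.36 (entry floor, halved) | 45% | 27% | 15% |

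The share left out passes one half at L of about 1.6. With more variation between subjects (negative binomial, k = 1), it passes one half at L = 1.0, and the range over the same cells is 25% to 86%. If every subject has exactly a treated attacks, the share is (a − 1)/a, which exceeds one half only when a is above 2.

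**What a display by attack number would hold.** Expected subjects at number k are 6 × P(count ≥ k):

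| L | 1st | 2nd | 3rd | 4th |
|---|---|---|---|---|
| 6.3 | 6.0 | 5.9 | 5.7 | 5.2 |
| 1.36 | 4.5 | 2.4 | 0.9 | 0.3 |

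At L = 6.3, three columns hold 6.0 + 5.9 + 5.7 = 17.6 of 6 × 6.3 = 37.8 treated attacks (47%), so attacks beyond the third also need a place.

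**Dependence.** A subject has one 1st treated attack, at most one 2nd, and so on. Within a column, each subject therefore appears at most once, and there is no within-subject dependence. Dependence arises only if columns are pooled.

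**Precision.** The widest order-statistic interval for a median, from minimum to maximum, has coverage 1 − 2 × 0.5ⁿ. That is 93.75% at n = 5 and 96.9% at n = 6. A column with fewer than 6 subjects cannot support an exact 95% interval.

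**The case against.** The strongest reply is that the quoted rule is correct and open. An ordinary Kaplan-Meier interval assumes independent observations, so one attack per subject is a proper choice, and the SAP gives its reason. This stands, and the first-attack analysis should not change.

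It is also true that later attacks are not lost. The rule is written for the time-to-event endpoint only. Average duration in SAP 5.7.1 runs from onset to complete resolution over all attacks in the treatment period, though it is not split by treatment or attack number. Listings 16.2.6.1 to 16.2.6.3 carry the attack data.

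Some stronger readings are tempting but unsupported:

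- **Most treated attacks are discarded.** The documents give no count. The 84% needs the overseas rate and every attack treated. Entry here requires about 2.8 attacks per 12 weeks, against 12.8 in the overseas placebo arm.
- **The result rests on at most six early attacks.** Six is a minimum number of completers, and the Full Analysis Set does not require completion. The first attack that meets the treatment criterion need not be early.
- **Dependence is the SAP's reason for dropping the display.** The SAP gives it only for the first-attack rule and gives no reason for the change of grouping.
- **First attacks are unrepresentative because Dosing Visits 1 to 8 are at the site.** Those visits concern scheduled doses. On-site treatment of attacks is recommended throughout, and a subject may qualify for self-administration before Visit 8. A difference between early and later attacks is possible but not shown.

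Finally, later columns contain only subjects with repeat attacks, so a comparison across columns mixes repeat response with selection. That stands, and it limits the display to description.

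**Conclusion.** The point holds as an undeclared departure from the protocol with a modest but real loss. The display by attack number has gone from the SAP's endpoints and planned outputs, and SAP 6.2 does not mention it. Every CINRYZE-treated attack after the first is left out of the time-to-event analysis, which is about 15% to 84% of treated attacks. That range rests on Poisson counts, 1.36 to 6.3 attacks per 12 weeks, and a quarter to all of them treated. Part of a stated objective, response on repeat treatment, is shown in no planned summary. The stated dependence supports the first-attack Kaplan-Meier analysis but does not preclude the protocol's display.

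**What to change.** Keep the first-attack Kaplan-Meier analysis as the main one. Add one descriptive table for CINRYZE-treated attacks that shows initial improvement, Complete Resolution and the time to each, with separate columns for the 1st, 2nd and 3rd treated attack. Put further attack numbers in their own columns or list them. Do not pool them into a 3rd-or-later column, which would bring dependence back or need a selection rule. Give no confidence interval for the median where a column has fewer than 6 subjects, and note that later columns include only subjects with repeat attacks.

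In SAP 6.2, declare both the change from attack number to treatment type and the first-attack restriction.

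The cost is one table from data already collected and two sentences of text. The downside is that the later columns will be small, and at the lower attack rates the 3rd column may be nearly empty.
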